5.4 CLAIMS

The REGENETEN Bioinductive Implant creates an environment that facilitates rotator cuff tendon repair [23, 24, 32, 33], supports the body's natural healing response to induce new tendon-like tissue growth and disrupt disease progression [23, 24, 33, 34, 35] and indicates a reduction in retear rates compared to standard of care [17, 24,].

.

CONFIDENTIAL AND PROPRIETARY

Study Protocol	Smith-Nephew
A Prospective, Multi-center, Randomized Controlled	Number:
Study to Evaluate the Safety and Efficacy of ARCR	REGENETEN.2020.01
augmented with REGENETEN™ Bioinductive Implant	Version: 2, 08 Dec 2021
System in Full-thickness Tears (large or massive) Repair versus ARCR alone	Page: 28 of 134

- 6. INVESTIGATIONAL PRODUCT(S)
- 6.1 IDENTIFICATION
- 6.1.1 Investigational Product
- 6.1.1.1 Description

The REGENETEN Implant System is a manual arthroscopic instrument that is used to assist in the arthroscopic delivery and placement of the Bioinductive Implant and is comprised of disposable instruments, a resorbable collagen implant, and anchors to secure the scaffold to the underlying tendon and bone (Figure 1).

MADE IN USA

2 3

Figure 1 REGENETEN Bioinductive Implant and Anchors

Shown from the left to right, Tendon Anchor, Bioinductive Implant and Bone Anchor

The REGENETEN Bioinductive Implant is a bioabsorbable implant that provides a layer of collagen over injured tendons. After hydration, the implant is an easy-to-handle, pliable, nonfriable, porous collagen sheet. The REGENETEN Bioinductive Implant is available in size large for the study. The collagen implant consists of a resorbable type I collagen matrix derived from bovine Achilles tendon. It is contraindicated for use in patients with a history of hypersensitivity to bovine-derived materials. The device is designed to completely resorb within 6 to 12 months.

CONFIDENTIAL AND PROPRIETARY

Study Protocol	Smith-Nephew
A Prospective, Multi-center, Randomized Controlled	Number:
Study to Evaluate the Safety and Efficacy of ARCR	REGENETEN.2020.01
augmented with REGENETEN™ Bioinductive Implant	Version: 2, 08 Dec 2021
System in Full-thickness Tears (large or massive) Repair versus ARCR alone	Page: 29 of 134

The REGENETEN Bioinductive Implant Delivery System is provided sterile, for single-use only in a dual sterile seal, tray-in-tray configuration.

The tendon anchors are made from poly (L-lactide-co-D,L-lactide) in a molar ratio of 70% L-lactide to 30% D,L-lactide. Polylactide materials have been used in a variety of medical devices, such as bone anchors, bone pins, screws, plates, and spinal fusion cages. The tendon anchors are intended for the fixation of prosthetic material to soft tissues and designed to completely absorb within approximately 12 months.

The bone anchors are made from polyetheretherketone (PEEK), which is a common polymer used for bone anchors in orthopedic surgery. The bone anchors are intended for fixation of soft tissue grafts. The bone anchors are not resorbable.

The disposable instrument system (Figure 2) includes the arthroscopic implant delivery instrument, tendon anchor delivery instruments, and bone anchor delivery instruments. There is also tendon markers and a tendon stabilizing guide that can be used if necessary but is not mandatory. The tendon guide wire is a useful tool for new and infrequent users.

CONFIDENTIAL AND PROPRIETARY

Study Protocol	Smith-Nephew
A Prospective, Multi-center, Randomized Controlled	Number:
Study to Evaluate the Safety and Efficacy of ARCR	REGENETEN.2020.01
augmented with REGENETEN™ Bioinductive Implant	Version: 2, 08 Dec 2021
System in Full-thickness Tears (large or massive) Repair versus ARCR alone	Page: 30 of 134

Figure 2 REGENETEN Disposable Instruments

Implant delivery instrument which comes with patch pre-loaded

Bone Anchor inserter

Tendon Anchor Inserter, Cannula, Tendon Anchors with Cartridge

The placement instruments include the Cannula Sleeve, Cannulas, Tendon Anchor Inserter, Bone Anchor Inserter, and Bone Punch. The Cannula Sleeve, Cannulas, and Tendon Anchor Inserters are used to place and deploy the Tendon Anchors. The Bone Anchor Inserter and Bone Punch are used to place the Bone Anchors.

CONFIDENTIAL AND PROPRIETARY

Study Protocol	Smith-Nephew
A Prospective, Multi-center, Randomized Controlled	Number:
Study to Evaluate the Safety and Efficacy of ARCR	REGENETEN.2020.01
augmented with REGENETEN™ Bioinductive Implant	Version: 2, 08 Dec 2021
System in Full-thickness Tears (large or massive) Repair versus ARCR alone	Page: 31 of 134

The Tendon Marker consists of a hypodermic needle that contains an internal anchor which advances to maintain the position of the marker. After insertion of the Tendon Marker, a slide on the handle is advanced to extend an anchor out of the shaft of the needle. Tendon Marker should only be used if available but are not mandatory.

The Tendon Stabilizing Guide consists of a flexible guide wire that is housed within the shaft of the instrument. After insertion of the guide wire into bone, the shaft of the instrument is removed and the guide wire is used to assist in guiding the Arthroscopic Delivery System to the proper location. The Tendon Stabilizing Guide is optional and can be used by new and infrequent users but is not mandatory.

Generation	Part#	Implant & Instrument SKU
US Gen 3.5	4566 4403 2504-1 4402 (1) 4173-1	Bioinductive Implant with Arthroscopic Delivery System, Large Bone Anchors with Delivery System Advanced Tendon Anchors (8) Tendon Stabilizing Guide Tendon Marker (2)
International Gen 3.0*	72205198 72205200 72205201 72205206 72205202	Large Arthroscopic Bioinductive Implant Bone Anchors (3) with Arthroscopic Delivery System Tendon Anchors (8) Tendon Stabilizing Guide (1) Tendon Marker (2)
International Gen 3.5	72205307 72205205 72205201 72205206 72205202	Bioinductive Implant with Arthroscopic Delivery System, Large Bone Anchors with Delivery System Advanced Tendon Anchors (8) Tendon Stabilizing Guide (1) Tendon Marker (2)

A complete description of the REGENETEN™ System is available in the IFUs and surgical technique documents provided by Smith+Nephew:

	Gen 3.5 US	Gen 3.5 Intl	Gen 3.0
Part	IFU Version	IFU Version	IFU Version
Bioinductive	02/2020 10601445	02/2020 10601447	02/2020 10601401
Implant	Rev. D	Rev. B	Rev. C
	01/2019 10601404	02/2020 10601391	02/2020 10601391
Tendon Anchors	Rev. B	Rev. C	Rev. C
	01/2019 10601405	02/2020 10601392	02/2020 10601392
Bone Anchors	Rev. B	Rev. C	Rev. C

CONFIDENTIAL AND PROPRIETARY

Study Protocol	Smith-Nephew
A Prospective, Multi-center, Randomized Controlled	Number:
Study to Evaluate the Safety and Efficacy of ARCR	REGENETEN.2020.01
augmented with REGENETEN™ Bioinductive Implant	Version: 2, 08 Dec 2021
System in Full-thickness Tears (large or massive) Repair versus ARCR alone	Page: 32 of 134

Tendon Stabilising	10/2018 10601407	02/2020 10601394	02/2020 10601393
Guide	Rev. A	Rev. C	Rev. C
	10/2018 10601408	02/2020 10601395	02/2020 10601395
Tendon marker	Rev. A	Rev. C	Rev. C
Manual Placement	05/2019 10601411	02/2020 10601399	02/2020 10601399
Instruments	Rev. B	Rev. D	Rev. D
Bioinductive			
Implant Delivery	02/2020 10601444	02/2020 10601448	02/2020 10601393
System	Rev. D	Rev. B	Rev. C

The IFUs may be updated periodically, in which case, the latest version will be used as a guide.

6.1.1.2 *Manufacturer*

The REGENETEN Bioinductive Implant manufacturer is:

Smith+Nephew Inc. [name] [name] USA

6.1.1.3 Intended Purpose

The REGENETEN Bioinductive Implant is indicated for the management and protection of rotator cuff tendon injuries in which there has been no substantial loss of tendon tissue.

Tendon Anchors are indicated for fixation of prosthetic material to soft tissues in various minimally invasive and open rotator cuff tendon surgical procedures, such as the management and protection of tendon injuries in which there has been no substantial loss of tendon tissue.

The Bone Anchor is indicated for fixation of soft tissue grafts during rotator cuff repair.

The Bioinductive Implant Delivery Instrument is indicated for arthroscopic delivery of the REGENETEN Bioinductive Implant into the subacromial space.

CONFIDENTIAL AND PROPRIETARY

Study Protocol	Smith-Nephew
A Prospective, Multi-center, Randomized Controlled	Number:
Study to Evaluate the Safety and Efficacy of ARCR	REGENETEN.2020.01
augmented with REGENETEN™ Bioinductive Implant	Version: 2, 08 Dec 2021
System in Full-thickness Tears (large or massive) Repair versus ARCR alone	Page: 33 of 134

The Manual placement instruments are orthopedic, manual, surgical instruments used during the placement of Bioinductive Implant, Bone Anchors, and Tendon Anchors.

The Tendon Stabilizing Guide is indicated for assisting in the arthroscopic placement and location of the Bioinductive Implant in the subacromial space. The Stabilizing Guide is not mandatory to be used.

The Tendon Marker is indicated for assisting in the arthroscopic placement and location of the Bioinductive Implant in the subacromial space. The Tendon Market is not mandatory to be used.

6.1.2 Comparator Treatment

Arthroscopic rotator cuff repair (ARCR) alone.

6.1.3 Ancillary Products

Arthroscopic measuring probe to confirm the tear size for eligibility (reusable).

6.2 PRODUCT USE

Each device is packaged with Instructions for Use and provided with surgical technique to ensure that the device is used properly and for the intended purpose as described in the specifications or IFUs or Investigator's Brochure (IB) (for China only). It is the Investigator's responsibility to ensure adherence to the IFU. Investigators must go through all steps of procedure at least once using all provided instruments on a test case, either in Arthroscopy Wet Lab or similar environment or real patient before enrollment. Investigators will be trained on the Investigational Product beforehand.

Recommended post-operative physical therapy guidelines for ARCR augmented with REGENETEN:

- Shoulder immobilization for 4-8 weeks,
- passive Range of Motion (PROM) begin at surgeon's discretion,

CONFIDENTIAL AND PROPRIETARY

Study Protocol	Smith-Nephew
A Prospective, Multi-center, Randomized Controlled	Number:
Study to Evaluate the Safety and Efficacy of ARCR	REGENETEN.2020.01
· ·	Version: 2, 08 Dec 2021
System in Full-thickness Tears (large or massive) Repair versus ARCR alone	Page: 34 of 134

- active Range of Motion (AROM) begin after sling is discontinued,
- no lifting >1-2 kg for 12-16 weeks,
- strengthening beginning after 12-16 weeks.

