6.3.1 Labeling of Investigational Product

The REGENETEN Bioinductive Implant System is an investigational product in China. Addition labels will be included on the commercial packaging to specify that the product is for clinical trial use only in order to meet regulatory requirements for use of investigational devices.

In the United States, Singapore, Hong Kong, Europe, Canada, Australia and New Zealand, the REGENETEN Bioinductive Implant System is a commercial product and will be used as cleared/licensed. Product labeling will be the same as per standard commercial packaging.

In Japan, the REGENETEN Bioinductive Implant System is a product that will be cleared/registered before study enrollment. The product will only be used either through market approval and/or special access approval.

For China only, labels on the REGENETEN Bioinductive Implant System contain the following information in addition to standard commercial packaging:

- Study number,
- Clinical Investigation Use Only.

Any regulatory status updates that may impact labeling requirements moving forward will be managed via TMP-CD-18-01 Investigational Products/Ancillary Products/Supplies Protocol.

CONFIDENTIAL AND PROPRIETARY

Study Protocol	Smith-Nephew
A Prospective, Multi-center, Randomized Controlled	Number:
Study to Evaluate the Safety and Efficacy of ARCR	REGENETEN.2020.01
augmented with REGENETEN™ Bioinductive Implant	Version: 2, 08 Dec 2021
System in Full-thickness Tears (large or massive) Repair versus ARCR alone	Page: 35 of 134

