6.5 SURGICAL TECHNIQUE

The REGENETEN System should be used according to the surgical technique and IFUs provided with the investigational device per Section 6.1.1.1

Investigators participating in this study must be proficient in arthroscopic rotator cuff repairs.

In addition, prior to implantation of the REGENETEN System, all principal surgical investigators involved in the REGENETEN procedure must be trained with respect to surgical technique, use of the device and surgical approach, so as to ensure consistency in the implementation of the clinical trial protocol and the use of the investigational device. Investigators must go through all

CONFIDENTIAL AND PROPRIETARY

Study Protocol	Smith-Nephew
A Prospective, Multi-center, Randomized Controlled	Number:
Study to Evaluate the Safety and Efficacy of ARCR	REGENETEN.2020.01
augmented with REGENETEN™ Bioinductive Implant	Version: 2, 08 Dec 2021
System in Full-thickness Tears (large or massive) Repair versus ARCR alone	Page: 36 of 134

steps of procedure at least once, using all provided instruments on a test case, either in Arthroscopy Wet Lab or similar environment or real patient before enrollment.

CONFIDENTIAL AND PROPRIETARY

Study Protocol	Smith-Nephew
A Prospective, Multi-center, Randomized Controlled	Number:
Study to Evaluate the Safety and Efficacy of ARCR	REGENETEN.2020.01
augmented with REGENETEN™ Bioinductive Implant	Version: 2, 08 Dec 2021
System in Full-thickness Tears (large or massive) Repair versus ARCR alone	Page: 37 of 134

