21.3 EQUIPMENT AND SPECIAL INSTRUCTIONS

Clinical study sites and PIs should properly manage the surgical tools, investigational devices and test equipment in accordance with regulations of applicable guidelines and trial protocol. The clinical study sites and the PIs cannot use and permit the use of the investigational devices and test equipment for any purpose other than the implementation of this trial, and will follow applicable guidelines, trial protocol and any instructions given by the Sponsor regarding any operation, maintenance or storage of the investigational devices and test equipment. Upon termination or expiration of this Agreement, according to the Sponsor's choice, all unused investigational devices and test equipment should be returned to the Sponsor or be disposed according to the written instructions of the Sponsor.

CONFIDENTIAL AND PROPRIETARY

Study Protocol	Smith-Nephew
A Prospective, Multi-center, Randomized Controlled	Number:
Study to Evaluate the Safety and Efficacy of ARCR	REGENETEN.2020.01
augmented with REGENETEN™ Bioinductive Implant	Version: 2.0, 08 Dec
System in Full-thickness Tears (large or massive) Repair	2021
	Page: 121 of 134

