- Article 64 The investigator shall ensure that all clinical trial participants are fully aware of the clinical trial protocol, relevant provisions, characteristics of the investigational medical device and the respective responsibilities in the clinical trial, that sufficient subjects who meet the selection criteria in the clinical trial protocol are involved in the clinical trial and that the time decided in the agreement is sufficient to safely implement and complete the clinical trial in accordance with relevant regulations during the trial period.
- Article 65 The investigator shall ensure that the investigational medical device is used only for the subjects of the clinical trial and shall not charge any fees.
- Article 66 The investigator shall strictly follow the clinical trial protocol and shall not deviate
 from the protocol or make a substantive change of plan without the consent of the sponsor
 and the ethics committee or the approval of China Food and Drug Administration in
 accordance with the regulations. However, when immediate treatment is needed in the face
 of emergencies such as direct danger to the subjects, the written report can be provided
 afterwards.
- Article 67 The investigator is responsible for recruiting subjects and talking with them or the
 guardians. The investigator shall explain to the subjects the details of the investigational
 medical device and details about the clinical trial, inform the subjects of possible benefits and
 known and foreseeable risks, and obtain signed and dated informed consent forms from the
 subjects or the guardians.
- Article 68 The investigators or other personnel involved in the trial shall not force or induce subjects to participate in the trial by any improper means.
- Article 69 If any unexpected adverse event incurred by the investigational medical device is
 found during the clinical trial, the investigator shall modify relevant content of the informed
 consent form with the sponsor, and the affected subjects or the guardians shall re-sign the
 modified informed consent form after it is reviewed and approved by the ethics committee in
 accordance with the relevant working procedures.

CONFIDENTIAL AND PROPRIETARY

Study Protocol	Smith-Nephew
A Prospective, Multi-center, Randomized Controlled	Number:
Study to Evaluate the Safety and Efficacy of ARCR	REGENETEN.2020.01
augmented with REGENETEN™ Bioinductive Implant	Version: 2.0, 08 Dec

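### Sections 6.2 and 6.5 let surgeons at China sites do the required practice case on a real patient, which Article 65 in section 21.6 does not allow

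*Combined protocol and SAP*

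**What the plan says.** Section 6.2 makes a practice case compulsory: "Investigators must go through all steps of procedure at least once using all provided instruments on a test case". The sentence goes on to say where it may be done, "on a test case, either in Arthroscopy Wet Lab or similar environment or real patient before enrollment". It thus accepts three settings, namely a wet lab, a similar environment, or a living patient treated before enrolment. Section 6.5 repeats the rule with the same list: "test case, either in Arthroscopy Wet Lab or similar environment or real patient before enrollment". Neither section limits the list by country.

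Section 6.3.1 sets out the regulatory status. "The REGENETEN Bioinductive Implant System is an investigational product in China", and extra labels are added there to "specify that the product is for clinical trial use only". The synopsis likewise describes the study as pre-market in China.

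Two appendix provisions restrict use of the device. Section 21.6, Article 65, in the China responsibilities, reads: "The investigator shall ensure that the investigational medical device is used only for the subjects of the clinical trial". Section 21.3, which is not limited to China, says that sites and principal investigators "cannot use and permit the use of the investigational devices and test equipment for any purpose other than the implementation of this trial". Section 13 obliges principal investigators to comply with the requirements set out in 21.5 and 21.6.

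**The concern.** For China, the protocol permits in one place what it forbids in another, and both provisions are operative. An investigator there could rely on 6.2 in good faith and still be in breach of Article 65. Article 66 adds to the difficulty by telling China investigators to follow the protocol strictly.

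The first stake is protection of the practice patient. Consent (7.5), eligibility screening (7.4), the visit schedule (9.1) and adverse event collection, which 8.3.4 starts at subject enrolment, are all written for trial subjects. A complication in a surgeon's first use of the device could leave no trace in the trial's safety data.

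The second stake is regulatory. The synopsis and section 8.1 still name registration in China as a use of this study, so an off-trial implant at a China site would be awkward to explain.

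**Working it through.** The point involves no figure and no calculation. The check is to set the provisions side by side and see whether they can all hold at a China site.

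1. **Is the practice case compulsory?** Yes. Sections 6.2 and 6.5 both say investigators must do it, covering all steps and all instruments supplied.
2. **Is a real patient an allowed setting?** Yes, expressly, in both sections. A case that covers all steps with all instruments includes placing the implant.
3. **Is China excepted?** No. Section 6.2 does carry a China-only remark, about the Investigator's Brochure, in the same paragraph. The drafters were therefore separating out China at that point but did not do so for the practice case.
4. **Would the practice patient be a trial subject?** Not on the text. Section 7.6 counts a person as enrolled only after consent, confirmed eligibility and study treatment. The practice case must come before enrolment, as a condition of the surgeon taking part. Nothing describes that patient as consented, screened or randomised.
5. **May the device be used in that patient in China?** Article 65 restricts the persons in whom it may be used to trial subjects. By step 4 the practice patient is not one, so use in that patient breaches Article 65.
6. **Does 21.3 give the same result?** Not by itself. It restricts the purpose of use, and training that the protocol itself requires can be argued to serve the trial. The firm conflict is with Article 65.
7. **Is the breach forced?** No. The three settings are alternatives, so a surgeon who uses a wet lab or similar environment meets 6.2, 6.5 and Article 65 together.

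**Size.** Let k be the number of China surgeons who must do a practice case. If each does one, the number of off-trial patients lies between 0 (all choose the wet lab or similar) and k (all choose a real patient). The documents give up to 30 sites across 13 listed countries or regions. They do not give the number of China sites, the number of surgeons per site, or the setting chosen, so k is unknown.

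**The case against.** The strongest reply is that nothing in 6.2 compels the conflict. The real patient is one option of three, and a specific China prohibition can be read as narrowing a general list. On that reading the option is simply unavailable in China, and the label and the device log in 6.4 point the same way. Much of this stands: it shows that the conflict is avoidable and that no off-trial implant should be predicted. It does not remove the inconsistency. Sections 6.2 and 6.5 are where a surgeon looks for the training rule, and they grant the option without qualification.

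A reader might go further than the documents allow in five ways:

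- **That following 6.2 means implanting an unapproved device off trial.** It does not, because the wet lab suffices.
- **That Japan has the same problem.** Section 6.3.1 says any use there will rest on market approval or special access approval, and Article 65 belongs to the China appendix.
- **That the protocol everywhere forbids use outside trial subjects.** Only Article 65 restricts persons. In the United States, Singapore, Hong Kong, Europe, Canada, Australia and New Zealand the device is commercial under 6.3.1, and a prior case there can be ordinary licensed use.
- **That device accountability necessarily fails.** A practice device could still be logged as used. The breach would be of Article 65.
- **That a patient count can be given.** Any count needs assumed numbers of sites and surgeons, and an assumption that they choose the real-patient option.

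One further point limits the safety concern. The adverse event definition in 12.1.1 extends to other persons for events related to the product, so a device-related complication in a practice patient is arguably within the definition. Even so, no consent, case report form or visit is provided through which it would be found.

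**Conclusion.** The point holds for China only. Sections 6.2 and 6.5 permit a real-patient practice case at China sites, and Article 65 rules it out. A China surgeon who took that option would breach Article 65, and the patient would lack the trial's consent, screening and follow-up and its collection of adverse events by subject.

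The conclusion rests on reading 7.6 as written, so that someone treated before enrolment is not a trial subject, and on section 13 giving 21.6 binding force. The number of patients affected is not derivable and may be zero; the sponsor can settle it by asking the China surgeons where they did their practice case. Randomisation, the primary endpoint, power and the analysis are unaffected. The sponsor should correct it because the text expressly permits a prohibited use in a patient and the correction is cheap.

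**What to change.** Reconcile 6.2 and 6.5 with 6.3.1, 21.3 and Article 65. Add one China-specific sentence to both 6.2 and 6.5, so that they no longer permit at China sites what Article 65 forbids. The wet-lab or similar setting already listed would meet the training requirement there, so no new training route is needed. Other countries need no change on this ground.

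The practical cost is scheduling wet-lab or similar sessions for any China surgeon who would otherwise have used a patient. Section 15 requires amendments to be approved before sites implement them, so the two sentences could go into the next planned amendment, with China sites told of the conflict in the meantime.

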4.4.4 Potential Adverse Effects

As with any surgery, this surgery will cause risks. Potential complications of this type of surgery include but are not limited to anesthesia complications; incision healing problems; trauma and bleeding; infection; failure of the repair or retear; nerve damage; vascular damage; pain or stiffness that persists; tissue inflammation.

Warnings and Precautions stated in the IFU:

Bioinductive Implant:

- Do no reuse or re-sterilize.
- Do not use if the product package is damaged or opened.
- The Bioinductive Implant should not be applied until bleeding and infection are controlled.
- Application of the Bioinductive Implant does not modify the postoperative treatment. The surgeon must determine motion and strength requirements according to standard practice.

CONFIDENTIAL AND PROPRIETARY

Study Protocol	Smith-Nephew
A Prospective, Multi-center, Randomized Controlled	Number:
Study to Evaluate the Safety and Efficacy of ARCR	REGENETEN.2020.01
ı	Version: 2, 08 Dec 2021
System in Full-thickness Tears (large or massive) Repair versus ARCR alone	Page: 25 of 134

Tendon Anchors:

- Do not use if the temperature indicator on the product packaging is black.
- Do not use if the product package is damaged or opened.
- Do not reuse or re-sterilize.
- Excessive force applied during anchor deployment may result in damage to the tissue, to the material being fixated, to the anchor.
- Overlapping anchors may result in damage to the anchor.

Bone Anchors:

- Do not use if the product package is damaged or opened.
- Do not reuse or re-sterilize.
- Excessive force applied during anchor deployment may result in damage to the tissue, to the material being fixated, to the anchor.
- Inserting the Bone Anchor through excessive soft tissue and failing to engage the anchor into bone may not provide adequate fixation.

Bioinductive Implant Placement Cannula:

- Do not use if the product package is damaged or opened.
- Do not reuse or re-sterilize.
- The cannula should be tapped lightly when inserting into bone. Do not drive the frame that holds the Bioinductive Implant into the bone.
- Do not advance cannula against resistance or damage to device may occur.

Manual Placement Instruments:

- Do not use if the product package is damaged or opened.
- Do not reuse or re-sterilize.

CONFIDENTIAL AND PROPRIETARY

Study Protocol	Smith-Nephew
A Prospective, Multi-center, Randomized Controlled	Number:

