7.4 SCREENING

The Investigators will continuously screen subjects during recruitment, which will continue until a total of up to 300 subjects (130 ACRC augmented with REGENETEN, 130 ARCR alone and up to 40 revision repair subjects) are recruited. It remains the decision of the Sponsor to increase or decrease enrollment, as necessary.

Once a subject has completed the informed consent procedure and signed the Informed Consent Form (IFU), the Principal Investigator (PI), or delegated study research staff, can complete the

CONFIDENTIAL AND PROPRIETARY

Study Protocol	Smith-Nephew
A Prospective, Multi-center, Randomized Controlled	Number:
Study to Evaluate the Safety and Efficacy of ARCR	REGENETEN.2020.01
augmented with REGENETEN™ Bioinductive Implant	Version: 2, 08 Dec 2021
System in Full-thickness Tears (large or massive) Repair versus ARCR alone	Page: 40 of 134

screening process to determine whether they meet all inclusion and none of the exclusion criteria. This might be the same day or another day, giving the subject enough time to consider participation.

Participating study sites are required to document all screened subjects considered for inclusion in this study on a Screening and Enrollment Log. If a subject is excluded from the study, the reasons for exclusion will be noted on the Screening and Enrollment Log.

In the event that a subject has the need for sequential bilateral ARCR augmented with REGENETEN or standard arthroscopic rotator cuff repair (ARCR), both shoulders may be enrolled in the study after informed consent process. Post-operative physical standard of care therapy guidelines and restrictions as stated in section 6.2 Product Use should be maintained for best outcome.

In the event that operation is delayed and outside Screening Visit Day time window, screening process has to be repeated to confirm eligibility.

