9.1.3 Operation – Visit 2 (Day 0)

- 1. Query subject regarding any changes in general health and the use of concomitant medications (e.g. oral or injected steroid use in last 4 weeks).
- 2. Confirm eligibility based on arthroscopic visualization of the tear and confirm size using a calibrated probe.
- 3. Assign the Randomization ID per randomization schedule. Screen Failure subjects should not be assigned randomization numbers, but their demographic information must be captured in the appropriate CRF with the reason for screen failure specified.
- 4. Commence operation as per the randomization schedule.
- 5. Collect operative and discharge data (including implant information) according to the CRF.
- 6. If any AEs, ADEs or DD are observed or reported, they must be recorded as instructed in Section 12 Adverse Events and Device Deficiencies.
- 7. Instruct the subject on proper postoperative care/procedures as per standard of care and/or Sponsor's recommendation given in section 6.2 Product Use.
- 8. Instruct the subject to document Opioid Use over the next 2 weeks on a daily basis.
- 9. Instruct the subject on follow-up procedures, including returning the treatment facility for follow-up at Visit 3 in 14 (± 5) days.

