- Total operative time will be calculated for each treatment arm and presented descriptively.
- The type of sling will be collected and presented for each treatment arm summarizing if standard sling, shoulder immobilizer, abduction sling, ER sling, or other were advised and mobilization time will be calculated for both arms summarizing mobilization duration.

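### The post-operative therapy guideline is headed for the REGENETEN arm only, and nothing in this open-label protocol requires equal rehabilitation in the two randomised arms

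*Combined protocol and SAP*

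**What the plan says.** - **Section 6.2 (Product Use)** introduces its list with "Recommended post-operative physical therapy guidelines for ARCR augmented with REGENETEN". The first item is "Shoulder immobilization for 4-8 weeks". Passive motion is left to the surgeon, and the items on active motion, lifting and strengthening follow.
- **Section 6.1.2 (Comparator Treatment)** reads, in full, "Arthroscopic rotator cuff repair (ARCR) alone". It has no rehabilitation text.
- **Section 4.4.4**, in the warnings taken from the instructions for use, says "Application of the Bioinductive Implant does not modify the postoperative treatment", and then "The surgeon must determine motion and strength requirements according to standard practice".
- **Section 7.4**, in the paragraph on subjects who need sequential bilateral repair with or without the implant, says "Post-operative physical standard of care therapy guidelines and restrictions as stated in section 6.2 Product Use should be maintained for best outcome".
- **Section 9.1.3, step 7**, tells the site: "Instruct the subject on proper postoperative care/procedures as per standard of care and/or Sponsor's recommendation given in section 6.2 Product Use". The step names no arm. It comes after the randomisation step of the same visit.
- **Section 8.2.2** states that the study is not blinded, and **section 9.1.11.2.1** places no restriction on concomitant therapies.
- **Sections 8.3.2 and 10.4.2** list sling type and mobilisation time as a secondary endpoint. For the latter, "mobilization time will be calculated for both arms summarizing mobilization duration".

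**The concern.** The stated objective is to compare repair with REGENETEN against repair alone. For a retear difference to be attributed to the implant, everything else done to the shoulder after randomisation should follow the same rule in both arms. The protocol itself treats rehabilitation as relevant to outcome, since section 7.4 gives best outcome as the reason for keeping to the 6.2 list.

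The only written rehabilitation guidance carries the name of one arm. Whoever gives the post-operative instruction knows the allocation. If a site follows the heading literally, its device subjects get the sponsor's list and its control subjects get whatever the site usually does. Any resulting difference in retear, pain, function or return to work would then be partly a rehabilitation effect. Analysis could not reliably remove it: rehabilitation is set after randomisation, and the primary model in section 10.4.1 adjusts for baseline characteristics only.

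**Working it through.** **1. What each section implies for each arm**

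| Section | REGENETEN arm | ARCR-alone arm |
|---|---|---|
| 6.2 heading | sponsor's list, recommended | not mentioned |
| 6.1.2 | – | nothing on rehabilitation |
| 4.4.4 | unchanged by the implant; surgeon's standard practice | – |
| 7.4 (bilateral cases only) | 6.2 list, called standard of care | 6.2 list, called standard of care |
| 9.1.3 step 7 | standard of care, 6.2 list, or both | same wording, but the 6.2 list is headed for the other arm |

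The 6.2 heading makes the guidance specific to one arm. Sections 4.4.4 and 7.4 point to common care. Section 9.1.3 does not settle the matter, because it offers both options without saying which applies to whom. Section 8.4, on minimising bias, does not mention rehabilitation, and no other section requires equal post-operative care.

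**2. Where bias could enter**

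Section 8.4.2 blocks the 1:1 allocation to balance it by site. Differences in routine *between* sites are therefore spread across both arms. Only different treatment of the two arms *within* a site can bias the comparison, and that is what an arm-specific heading in an open-label trial makes possible.

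**3. Size**

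The documents give no effect of rehabilitation on retear, so every shift below is an assumption. The inputs from section 11 are 15% versus 30% retear, 130 per arm and 80% power at 5%; section 10.1 makes tests two-sided.

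Formula (single look, normal approximation): power = Φ[(|p2 − p1| − 1.96 × SE0) / SE1], with SE0 = √[2p̄(1 − p̄)/n] and SE1 = √{[p1(1 − p1) + p2(1 − p2)]/n}.

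*The plan's own figure.* For 15% versus 30% with n = 130: p̄ = 0.225, SE0 = 0.0518, SE1 = 0.0510, so (0.15 − 0.1015)/0.0510 = 0.95 and power = 82.9%. Fisher's exact test gives 79.7%, in line with the stated 80%. The sample size is not in question here.

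*Implant has no effect, and rehabilitation alone lowers device-arm retear from 30%.* Worked case, 5 points: p̄ = 0.275, SE0 = 0.0554, SE1 = 0.0553, so (0.05 − 0.1085)/0.0553 = −1.06 and the probability is 14.5%.

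| Assumed shift (points) | Device-arm retear | Chance of false superiority (nominal 2.5%) |
|---|---|---|
| 2 | 28% | 5.4% |
| 3 | 27% | 7.7% |
| 5 | 25% | 14.5% |
| 8 | 22% | 31.2% |
| 10 | 20% | 46.1% |

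*Implant works as planned (15% versus 30%), and rehabilitation raises device-arm retear.*

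| Assumed shift (points) | Device-arm retear | Power |
|---|---|---|
| 0 | 15% | 82.9% |
| 2 | 17% | 69.8% |
| 3 | 18% | 62.1% |
| 5 | 20% | 46.1% |

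The tables show how sensitive the primary test is to a given imbalance. They are not evidence that any imbalance will occur.

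**The case against.** A reader might go further and infer that control subjects are assigned to site routine while device subjects are assigned to the sponsor's guideline, so that the trial does compare implant plus guideline with repair plus local care. The documents do not support that. Step 7 of section 9.1.3 applies to every operated subject and offers the same choice in both arms. Section 4.4.4 puts standard practice in charge in the device arm as well, and section 6.2 makes the investigator responsible for following the instructions for use. Section 7.4 calls the 6.2 list standard of care for either procedure.

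The list is also a weak instruction. It is only recommended, its ranges are wide (4–8 and 12–16 weeks), and it leaves passive motion to the surgeon. Its place in the investigational product section may explain why the heading names the device. Nothing shows that ordinary site practice falls outside it. Sling type and mobilisation time are summarised in both arms, and section 9.1.11.2.2 records therapies related to the study treatment, so an imbalance would be at least partly visible.

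All of this stands against the stronger reading. It does not close the gap. The 7.4 text covers bilateral cases only, the arm-neutral step refers to a list headed for one arm, and no section requires equal care. Seeing an imbalance afterwards would not undo it, because adjusting for a variable set after randomisation does not by itself remove the bias.

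**Conclusion.** The point holds as a contradiction that leaves room for bias, not as a demonstrated confounding of implant with rehabilitation. Section 6.2 conflicts with sections 4.4.4 and 7.4, and section 9.1.3 does not resolve the conflict. In an open-label trial with no equal-care rule, post-operative care may differ by arm within a site, and the 6-month retear comparison could be biased in favour of the device or against it.

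No size can be derived from the documents. The figures above rest on assumed shifts, 130 per arm with complete data, the planning rates and a single-look test. They show that a shift of a few points would matter. The point deserves action because a wording change can prevent the problem, whereas analysis cannot reliably repair it.

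**What to change.** Reconcile sections 6.2, 4.4.4, 7.4 and 9.1.3 so that the post-operative instruction does not depend on the randomised arm, and say so explicitly in step 7 of section 9.1.3. Whether the common instruction is a written guideline or site standard practice, and what it contains, is for the clinicians to settle.

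Keep sling type and mobilisation time as listed secondary endpoints. In addition, pre-specify that they will be reported by arm as a check of equal co-treatment.

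The cost is a protocol wording change and a memo to sites, using data already collected and adding no visits. The small downside is that sites lose some freedom to vary rehabilitation by arm.
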